7.7.1.1.2. Tumor Imaging During the Study

The first imaging assessment should be performed 8 weeks after the first dose of study drug, every 8 weeks (56 days \pm 7 days) for 12 months, and then every 12 weeks (84 days \pm 7 days) thereafter until disease progression is determined. Imaging assessments may be performed more frequently if clinically indicated. **Imaging should not be adjusted for delays in cycle starts.**

Per mRECIST v1.1, response should be confirmed by a repeat radiographic assessment not less than 4 weeks from the date that the response was first documented. The scan for confirmation of response may be performed at the earliest of 4 weeks after the first indication of response or at the next scheduled scan, whichever is clinically indicated.

Imaging should continue to be performed until documented disease progression, the start of new anticancer treatment, withdrawal of consent, death, or the end of the study, whichever occurs first. Disease progression should be confirmed at least 4 weeks, but no later than 6 weeks after the first scan indicating progression in clinically stable subjects. Subjects who have unconfirmed disease progression may continue on treatment until progression is confirmed, provided that they have met the conditions detailed in [Section 7.7.1](#). A central imaging vendor will not be used in this study.

7.7.1.1.3. Imaging During Follow-Up

If the subject discontinues study drug for reasons other than disease progression, imaging assessments should continue at the Protocol-specified interval until documented disease progression, the start of new anticancer treatment, withdrawal of consent, death, or the end of the study, whichever occurs first.

7.8. Performance and Quality-of-Life Assessments

Eastern Cooperative Oncology Group performance status ([Appendix C](#)) must be assessed by a medically qualified individual and recorded in the CRF at visits indicated in [Table 7](#).

7.9. Pharmacokinetic Assessments

7.9.1. Blood Sample Collection

[figure not shown]
Pharmacokinetics [REDACTED] samples will be obtained at the visits indicated in [Table 9](#). Timing of PK [REDACTED] assessments are outlined in [Table 13](#). After the predose PK sample is drawn, subjects will begin the study drug infusion. Predose is defined as within 24 hours before administration of study drug. Adjustments to the timing of blood sampling may be made based on emerging PK data. The exact dates and times of the PK blood collection will be recorded in the eCRF. Instructions for sample preparation and shipping will be provided in the Laboratory Manual.

[figure not shown]
Table 13: Timing of Pharmacokinetic [REDACTED] Sample Collection

[figure not shown]
Study Visit	Assessment	Timing of Sample Collection
Cycle 1 Day 1	PK [REDACTED]	• Preinfusion
	PK	• Postinfusion (\pm 10 min) • 4 h (\pm 30 min) postinfusion
Cycle 1 Day 2	PK	• 24 h (\pm 60 min) postinfusion
Cycle 1 Day 7	PK	• Untimed PK sample
Cycle 2 Day 1	PK [REDACTED]	• Preinfusion
Cycle 3 Day 1	PK [REDACTED]	• Preinfusion
Cycle 4 Day 1	PK	• Preinfusion
Cycle 6 Day 1	PK [REDACTED]	• Preinfusion
	PK	• Postinfusion (\pm 10 min) • 4 h (\pm 30 min) postinfusion
Cycle 6 Day 2	PK	• 24 h (\pm 60 min) postinfusion
Cycle 6 Day 7	PK	• Untimed PK sample
Cycle 7 Day 1	PK	• Preinfusion
[REDACTED]	[REDACTED]	[REDACTED]

[figure not shown]
7.9.2. Pharmacokinetic Analysis

The PK calculations will be performed, if appropriate, using commercial software such as WinNonlin® (Pharsight Corporation, Mountain View, CA). Nominal times will be used in all cases, except when the difference between the actual time and nominal time is greater than 5 minutes for samples collected up to 4 hours after administration; in these cases, actual times will be used for PK analysis. Additional details of analyses will be described in the Statistical Analysis Plan.

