Reference Therapy, Dosage, and Mode of Administration:

Not applicable.

Study Schedule/Procedures:

Subjects will have regularly scheduled study visits at the clinical site on Day 1 of each cycle. Additional study visits may be required during some cycles to monitor for safety, efficacy, or for PK/■ evaluations. Study visits are as follows:

- **Screening:** up to 28 days before enrollment. Screening will begin at the time that the subject signs the informed consent and will continue until the date that the subject is enrolled in the study (Cycle 1 Day 1).
- **Cycle 1:** Day 1, Day 2, and Day 7 (± 1 day).
- **Cycle 2:** Day 1 (± 1 days) and Day 7 (± 1 day).
- **Cycle 6:** Day 1 (± 3 days), Day 2, and Day 7 (± 1 day).
- **All other treatment cycles:** Day 1 (± 3 days).
- **Efficacy assessments:** Every 8 weeks (± 7 days) for 12 months, and every 12 weeks (± 7 days) thereafter until disease progression is determined.

- **End of treatment:** \pm 3 days of withdrawal from study.
- **Safety follow-up:** 30 days (+ 7 days) and 60 days (+ 7 days) after end of treatment.

Safety Assessments:

Subjects will have regularly scheduled study visits at the clinical site on Day 1 of every cycle where targeted physical examinations, vital sign collection, ECOG performance status, collection of concomitant medications, and AE assessments will be performed. A 12-lead ECG will be performed at screening, Cycle 1 Day 1, Cycle 2 Day 1, and then Day 1 of **every other cycle** after Cycle 2 (eg, Cycle 4, Cycle 6, Cycle 8). Triplicate ECG measurements will be performed at screening, Cycle 1 Day 1, and Cycle 6 Day 1, in conjunction with PK assessments. Laboratory assessments will be collected on Day 1 of each cycle, with more frequent blood sample collection during the first and second cycles (Day 1 and Day 7) to evaluate for DLTs. Toxicities will be monitored continuously and will be graded using the NCI CTCAE v4.03 criteria.

On Day 1 of the first 4 cycles (Cycle 1 Day 1, Cycle 2 Day 1, Cycle 3 Day 1, and Cycle 4 Day 1), subjects will be required to stay at the study site for at least 4 hours after infusion of study drug for safety observation. It is recommended that the subject does not leave the site for any reason during the safety observation period. During the safety observation period, subjects will be assessed for the onset of acute AEs.

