7.6. Pharmacokinetic Analyses

[figure not shown]
[figure not shown]
The PK calculations will be performed, if appropriate, using commercial software such as WinNonlin® (Pharsight Corporation, Mountain View, CA). Nominal times will be used in all cases, except when the difference between the actual time and nominal time is greater than 5 minutes for samples collected up to 4 hours after administration; in these cases, actual time will be used for PK analysis.

The PK parameters of C_{max} , t_{max} , C_{min} , and AUC_{0-t} (INCAGN01949) will be summarized by part, dose, and study cycle. The log-transformed PK parameters will be compared among dose levels by using a 1-factor analysis of variance. Dose-dependent parameters (C_{max} and AUC) will be normalized to the lowest common dose before statistical comparisons. Additionally, if sufficient data are available, the dose proportionality of INCAGN01949 C_{max} and AUC will be evaluated statistically by using a power model (eg, $AUC = \alpha \cdot (dose)^\beta$) or equivalently $\log(AUC) = \log(\alpha) + \beta \cdot \log(dose)$, where linear dose proportionality is accepted if β is not significantly different from 1).

If there is a sufficient amount of plasma concentration data from this study, then the data will be analyzed by standard population PK methods using appropriate software (eg, NONMEM). The effect of covariates on PK parameters will be evaluated. The covariates will include, but not be

limited to, demographics (age, weight, sex, race), clinical laboratory test values, and concomitant medications.

The relationship between plasma concentrations of INCAGN01949 and the baseline-subtracted change in QTc interval will be explored graphically and analyzed using a linear mixed-effect model.

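### AUC0-t is computed from nominal times for the Day 7 and next-cycle preinfusion samples, whose windows are 1 to 3 days, although exact times are recorded

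*Protocol*

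**What the plan says.** Protocol 7.9.2 makes nominal time the default: "Nominal times will be used in all cases, except when the difference between the actual time and nominal time is greater than 5 minutes". In full, it switches to actual time only when the deviation is "greater than 5 minutes for samples collected up to 4 hours after administration; in these cases, actual times will be used for PK analysis". It leaves further detail to the SAP. SAP 7.6 gives the same rule: nominal times in all cases, except deviations of more than "5 minutes for samples collected up to 4 hours after administration; in these cases, actual time will be used for PK analysis". Neither document has a separate provision for later samples.

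The later samples are listed in Protocol Table 13, with visit windows in the Synopsis (Study Schedule/Procedures) and Table 9:

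- 24 h after infusion in Cycles 1 and 6: ±60 min.
- Day 7 in Cycles 1 and 6: visit window ±1 day, described in Table 13 as "Untimed PK sample".
- Preinfusion on Day 1 of Cycle 2: ±1 day. Preinfusion on Day 1 of Cycles 3, 4, 6 and 7: ±3 days. Section 7.9.1 also lets a predose sample be drawn up to 24 h before the infusion.

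On recording, Protocol 7.9.1 is explicit: "The exact dates and times of the PK blood collection will be recorded in the eCRF".

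AUC0-t is a secondary endpoint (Protocol 2.2.2, SAP 2.3.2). Protocol 9.4.3 and SAP 7.6 use AUC in a one-factor analysis of variance across dose levels and in a power model for dose proportionality.

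**The concern.** The rule corrects a six-minute deviation at 4 hours and ignores one of up to three days at the next preinfusion sample. For an antibody with a half-life of many days, most of AUC0-t lies between the 24 h sample and the last sample, so the uncorrected times are the ones that carry the area. For Day 7 the rule is also incomplete: a sample with no scheduled clock time has no nominal time to apply. SAP 4.1.5 accepts that cycles may drift from 14 days, but the PK rule makes no allowance for it.

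What is at stake is avoidable scatter in a secondary endpoint, in dose cohorts of 3 to 6 subjects. If dosing is delayed, there is also an error that runs in one direction.

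**Working it through.** **Inputs.** Monkey PK from Protocol 1.2.2: clearance 0.23 mL/h/kg, volume 90.3 mL/kg, half-life 11.4 days. Protocol 1.2.3 gives about 15 days after repeat dosing. Windows are as listed above.

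**Reproducing the plan's figure.** ln 2 × 90.3 / 0.23 = 272 h = 11.34 days, against 11.4 stated (0.5% apart). The documents give no figure for AUC error.

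**Assumptions.** Human half-life as in the monkey; one compartment; log-trapezoidal AUC; nominal times 0, 4 h, 24 h, 6 days (Day 7) and 14 days (next preinfusion). The 6 and 14 day values are assumed, because Table 13 gives neither. It is also assumed that the next preinfusion sample closes the AUC.

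**Formula.** With C(t) = exp(-kt) and k = ln 2 / 11.4 = 0.0608 per day, the log-trapezoid on actual times gives (C_i - C_j)/k for each segment. Plotting the same concentrations at nominal times multiplies each segment by its nominal length over its actual length. The common factor 1/k is dropped below.

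Concentrations used: C(1) = 0.9410, C(5) = 0.7379, C(6) = 0.6943, C(7) = 0.6534, C(11) = 0.5123, C(13) = 0.4536, C(14) = 0.4269, C(15) = 0.4017, C(17) = 0.3557. The fixed 0 to 14 day AUC is 1 - 0.4269 = 0.5731.

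*Example: Cycle 6, next preinfusion sample 3 days early (day 11).* Actual: 1 - 0.5123 = 0.4877. Nominal: (1 - 0.6943) + (0.6943 - 0.5123) × 8/5 = 0.5969. Ratio 1.224.

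*Example: Cycle 1, both samples 1 day late (days 7 and 15).* Actual: 1 - 0.4017 = 0.5983. Nominal: (1 - 0.9410) + (0.9410 - 0.6534) × 5/6 + (0.6534 - 0.4017) × 8/8 = 0.5504. Ratio 0.920.

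| Case (half-life 11.4 days) | Actual-time AUC to last sample | Nominal-time AUC | Nominal vs actual | Nominal vs fixed 0-14 d | Actual (to last sample) vs fixed 0-14 d |
|---|---|---|---|---|---|
| Cycle 1, Day 7 and C2D1 both 1 day early | 0.5464 | 0.5971 | +9.3% | +4.2% | -4.7% |
| Cycle 1, both 1 day late | 0.5983 | 0.5504 | -8.0% | -4.0% | +4.4% |
| Cycle 6, C7D1 3 days early | 0.4877 | 0.5969 | +22.4% | +4.2% | -14.9% |
| Cycle 6, C7D1 3 days late | 0.6443 | 0.5519 | -14.3% | -3.7% | +12.4% |

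At 15 days the nominal-versus-actual errors are similar: +8.9%/-7.7% in Cycle 1 and +23.5%/-15.1% in Cycle 6. If Day 7 is the last quantifiable sample, a 1-day shift gives +19.4% (early) or -13.8% (late) at 11.4 days. Moving the 24 h sample by 60 min changes AUC by 0.07%.

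**Expected scatter.** With deviations uniform over the windows (20,000 simulated subjects, 11.4 days), the per-subject error in AUC to the last sample has SD 3.7% in Cycle 1 and 10.6% in Cycle 6, with mean +0.1% and +1.4%.

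**One-sided error.** If a dose delay puts C7D1 at day 28 (C = 0.1822), nominal AUC is 0.3057 + (0.6943 - 0.1822) × 8/22 = 0.4919. That is 40% below actual-time AUC to that sample (0.8178) and 14% below the fixed 0 to 14 day AUC.

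**The case against.** The strongest reply is that the quoted ratios exaggerate the harm. They are window-edge values, and they compare with AUC to whatever moment the last sample was drawn. Against a fixed 14-day exposure, nominal placement is off by only about 4%. Simply substituting actual times would make subjects less comparable: the last column of the table shows -15% to +12% for a 3-day shift, because each AUC then covers a different interval. This stands, and it changes the remedy: actual times need to be paired with a common interval.

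The effect on the power model is also small. Doses run from 7 to 1400 mg; with 3 subjects at each of 7 levels, the sum of squares of ln(dose) is about 66. The scatter adds about 0.037/√66 = 0.005 (Cycle 1) or 0.106/√66 = 0.013 (Cycle 6) to the standard error of the slope. PK is secondary, SAP 3.3 calls all analyses exploratory, and no escalation or Simon rule uses AUC numerically. A pharmacokineticist reviews sample records (SAP 5.3.5.1), but only to identify exclusions.

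A reader might infer three further harms that the documents do not support:

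- That every sample after 4 h has a window of days. The 24 h sample has ±60 min and negligible effect.
- That Cmin is distorted. The SAP abbreviation list defines it as an observed minimum, and a time label does not change an observed value. Cmax comes mainly from early samples, which the exception protects.
- That the population PK analysis runs on nominal times. It is conditional on sufficient data, and its time basis is not stated.

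**Conclusion.** The point holds for AUC0-t and for the Day 7 and next-cycle preinfusion samples. The rule is explicit in both documents, nothing overrides it, and the data that would remove the error are already collected. For AUC to the last sample, the window-edge error is about -8% to +9% in Cycle 1 and -14% to +22% in Cycle 6, with a per-subject SD of about 4% and 11%. Against a fixed 0 to 14 day AUC it is about ±4%.

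These sizes rest on a monkey half-life, one compartment, and nominal times of 6 and 14 days that the documents do not give. That the error is avoidable does not depend on those assumptions.

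It would be tempting to conclude that the dose-proportionality result is biased. The documents do not support that. Within symmetric windows the error is almost entirely scatter. It becomes one-sided only if delays occur, which Protocol 5.4.6 permits, and it would distort dose comparisons only if delays differed by dose, which cannot be known from the plan.

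**What to change.** In Protocol 7.9.2 and SAP 7.6:

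1. Use actual elapsed time since dosing for all postdose samples in the AUC calculations, including Day 7 and the next preinfusion sample. Keep nominal times for by-visit labels, or when the actual time is missing.
2. For the dose-level comparison and the power model, compute AUC over a common interval, for example 0 to 14 days for the 14-day schedule, by interpolation or short extrapolation from the actual times.
3. State which sample closes the AUC in each cycle, and the time basis of the population PK analysis.

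The cost is wording and minor programming. No new data are needed.

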7.11. Other Study Procedures

7.11.1. Distribution of Subject Reminder Cards

Subjects will be provided with a reminder card at each visit. The subject reminder cards will remind the subject of the date/time of the next visit.

8. SAFETY MONITORING AND REPORTING

8.1. Adverse Events

8.1.1. Definitions

For the purposes of this Protocol, an adverse event (AE) is defined as any untoward medical occurrence associated with the use of a drug in humans, whether or not considered drug related, that occurs after a subject provides informed consent. Abnormal laboratory values or test results occurring after informed consent constitute AEs only if they induce clinical signs or symptoms, are considered clinically meaningful, require therapy (eg, hematologic abnormality that requires transfusion), or require changes in the study drug(s).

8.1.2. Reporting

Adverse events that begin or worsen after informed consent should be recorded on the Adverse Events form of the eCRF. Conditions that were already present at the time of informed consent should be recorded on the Medical History form in the eCRF. Monitoring for the occurrence of new AEs should be continued for at least 60 days after the last dose of study drug or until the start of new anticancer therapy, whichever occurs first. Adverse events (including laboratory abnormalities that constitute AEs) should be described using a diagnosis whenever possible rather than by individual underlying signs and symptoms.

The term "disease progression" should be recorded as an AE/SAE only if there are no other identifiable AEs/SAEs associated with the disease progression at the time of reporting. For events associated with disease progression, the relevant signs and symptoms should be reported using a diagnosis whenever possible rather than individual underlying signs and symptoms. When a clear diagnosis cannot be identified, each sign or symptom should be reported as a separate AE. If the events resulting from disease progression meet the criteria for an SAE (eg, resulted in hospitalization, a life-threatening event, or death), the specific event(s) should be reported as an SAE(s) as described in [Section 8.3.2](#). In both cases (ie, AEs or SAEs related to disease progression), it should be indicated that each event (reported as a diagnosis or as signs and symptoms) is related to disease progression on the Adverse Events form of the eCRF.

The severity of AEs will be assessed using CTCAE v4.03 Grades 1 through 4. The CTCAE v4.03 severity of Grade 5 will not be used; AEs resulting in death will be graded accordingly using Grades 1 through 4 and have the outcome noted as fatal. If an event is not classified by CTCAE, the severity of the AE will be graded according to the scale below to estimate the grade of severity:

Grade 1	Mild; asymptomatic or mild symptoms; clinical or diagnostic observations only; intervention not indicated.
Grade 2	Moderate; minimal, local, or noninvasive intervention indicated; limiting age-appropriate activities of daily living.
Grade 3	Severe or medically significant but not immediately life-threatening; hospitalization or prolongation of hospitalization indicated; disabling; limiting self-care activities of daily living.
Grade 4	Life-threatening consequences; urgent intervention indicated.

The occurrence of AEs should be sought by nondirective questioning of the subject during the screening process after signing the ICF and at each visit during the study. Adverse events may also be detected when they are volunteered by the subject during the screening process or between visits, or through physical examination, laboratory test, or other assessments. To the extent possible, each AE should be evaluated to determine:

- The severity grade (CTCAE Grade 1 to 4).
- Whether there is at least a reasonable possibility that the AE is related to the study treatment: suspected (yes) or not suspected (no).
- The start and end dates, unless unresolved at final follow-up.
- The action taken with regard to study drug.
- The event outcome (eg, not recovered/not resolved, recovered/resolved, recovering/resolving, recovered/resolved with sequelae, fatal, unknown).
- The seriousness, as per serious adverse event (SAE) definition provided in [Section 8.3.1](#).

Unlike routine safety assessments, SAEs are monitored continuously and have special reporting requirements (see [Section 8.3.2](#)).

All AEs should be treated appropriately. If an AE is treated with a concomitant medication or nondrug therapy, this action should be recorded on Adverse Event form and the treatment should be specified on the Prior/Concomitant Medications or Procedures and Non-Drug Therapy form in the eCRF.

Once an AE is detected, it should be followed until it has resolved or until it is judged to be permanent; assessment should be made at each visit (or more frequently if necessary) of any changes in severity, the suspected relationship to the study drug, the interventions required to treat the event, and the outcome.

When the severity of an AE changes over time for a reporting period (eg, between visits), each change in severity will be reported as a separate AE until the event resolves. For example, 2 separate AEs will be reported if a subject has Grade 1 diarrhea, meeting the definition of an

AE, that lasts for 3 days before worsening to a Grade 3 severity. The Grade 1 event will be reported as an AE with a start date equal to the day the event met the Grade 1 AE definition and a stop date equal to the day that the event increased in severity from Grade 1 to Grade 3. The Grade 3 event will also be reported as an AE, with the start date equal to the day the event changed in intensity from Grade 1 to Grade 3 and a stop date equal to the day that the event either changed severity again or resolved.

8.2. Laboratory Test Abnormalities

Laboratory abnormalities that constitute an AE in their own right (considered clinically meaningful, induce clinical signs or symptoms, require concomitant therapy, or require changes in study drug) should be recorded on the Adverse Event form in the eCRF. Whenever possible, a diagnosis rather than a symptom should be provided (eg, "anemia" instead of "low hemoglobin"). Laboratory abnormalities that meet the criteria for AEs should be followed until they have returned to normal or an adequate explanation of the abnormality is found. When an abnormal laboratory test result corresponds to a sign or symptom of a previously reported AE, it is not necessary to separately record the laboratory test result as an additional event.

Laboratory abnormalities that do not meet the definition of an AE should not be reported as AEs. A Grade 3 or 4 (severe) AE does not automatically indicate an SAE unless it meets the definition of serious, as defined in [Section 8.3.1](#). A dose modification for the laboratory abnormality may be required (see [Section 5.4](#)) and should not contribute to the designation of a laboratory test abnormality as an SAE.

8.3. Serious Adverse Events

8.3.1. Definitions

An SAE is defined as an event that meets at least 1 of the following criteria:

- Is fatal or life-threatening.
- Requires inpatient hospitalization or prolongation of existing hospitalization, unless hospitalization is a result of:
 - A routine treatment or monitoring of the studied indication not associated with any deterioration in condition.
 - An elective surgery or preplanned treatment for a pre-existing condition that is unrelated to the indication under study and has not worsened since signing the ICF.
 - A treatment on an emergency outpatient basis for an event not fulfilling any of the definitions of a SAE and not resulting in hospital admission.
 - Any social reasons and respite care, in the absence of any deterioration in the subject's general condition.
- Results in persistent or significant disability, incapacity, or a substantial disruption of a person's ability to conduct normal life functions.

- Constitutes a congenital anomaly or birth defect.
- Is considered to be an important medical event or a medically significant event that may not result in death, be immediately life-threatening, or require hospitalization but may be considered serious when, based on appropriate medical judgment, the event may jeopardize the subject or may require medical or surgical intervention to prevent 1 of the outcomes listed above.

